8.2 Recording of Adverse Events

At each contact with the subject, the study team must seek information on adverse events by specific questioning and, as appropriate, by examination. Information on all adverse events should be recorded immediately in the source document, and also in the appropriate adverse event section of the case report form (CRF). All clearly related signs, symptoms, and abnormal diagnostic, laboratory or procedure results should recorded in the source document.

All adverse events occurring during the study period must be recorded. The clinical course of each event should be followed until resolution, stabilization, or until it has been ultimately determined that the study treatment or participation is not the probable cause. Serious adverse events that are still ongoing at the end of the study period must be followed up, to determine the final outcome. Any serious adverse event that occurs during the Adverse Event Reporting Period and is considered to be at least possibly related to the study treatment or study participation should be recorded and reported immediately.

8.3 Reporting of Serious Adverse Events and Unanticipated Problems

When an adverse event has been identified, the study team will take appropriate action necessary to protect the study participant and then complete the Study Adverse Event Worksheet and log. The sponsor-investigator will evaluate the event and determine the necessary follow-up and reporting required.

Relationship of adverse events to study drug

For all AEs, the investigator will assess the causal relationship between the study drug and the AE using his/her clinical expertise and judgment according to the following algorithm that best fits the circumstances of the AE. The investigator will interpret and document whether or not an AE has a reasonable possibility of being related to study treatment, study device, or a study procedure, taking into account the disease, concomitant treatment or pathologies. A "reasonable possibility" means that there is a cause and effect relationship between the investigational product, study device and/or study procedure and the AE. The investigator answers yes/no when making this assessment.

Planned surgeries and nonsurgical interventions should not be reported as AEs unless the underlying medical condition has worsened during the course of the study.

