To ensure patient safety, every SAE, regardless of causality, occurring after the patient has provided informed consent and until 30-days after the subject stopped study participation must be reported to Eli Lilly and Company as soon as possible but no later than 5 days from learning of its occurrence according to the Mayo Clinic IRB policy. Any SAEs experienced after the 30-days period should only be reported to Eli Lilly and Company and the Mayo Clinic IRB if the investigator suspects a causal relationship to study treatment. Recurrent episodes, complications, or progression of the initial SAE must be reported as follow-up to the original episode, regardless of when the event occurs. This report must be submitted as soon as possible but no later than 5 days from the investigator receiving the follow-up information. SAE should be followed up until resolution or until it is judged to be permanent. An SAE that is considered completely unrelated to a previously reported one should be reported separately as a new event.

Information collected on the adverse event worksheet (and entered in the research database):

- Subject's name:
- Medical record number:
- Disease/histology (if applicable):
- The date the adverse event occurred:
- Description of the adverse event:
- Relationship of the adverse event to the research (drug, procedure, or intervention*):
- If the adverse event was expected:
- The severity of the adverse event: (use a table to define severity scale 1-5**)
- If any intervention was necessary:
- Resolution: (was the incident resolved spontaneously, or after discontinuing treatment)
- Date of Resolution:

AE Reporting:

Its relationship to the:

- Study treatment (no/yes), or
- Investigational treatment (no/yes), or
- The other study treatment (non-investigational) (no/yes), or
- Both or indistinguishable

The relationship will be categorized as follows:

- Unrelated- Clearly due only to extraneous causes and does not meet criteria listed under possible or probable.
- Unlikely- Does not follow a reasonable temporal sequence from administration. May have been produced by the patient's clinical state or by environmental factors or other therapies administered.
- Possible- Follows a reasonable temporal sequence from administration but may have been also produced by the patient's clinical state, environmental factors or other therapies administered.

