8.3.2 Sponsor-Investigator reporting: Notifying the FDA and Funding Sponsor

The sponsor-investigator will report to the FDA all unexpected, serious suspected adverse reactions according to the required IND Safety Reporting timelines, formats and requirements.

Unexpected fatal or life threatening suspected adverse reactions where there is evidence to suggest a causal relationship between the study drug/placebo and the adverse event, will be reported as a serious suspected adverse reaction. This will be reported to the FDA on FDA Form 3500A, no later than 7 calendar days after the sponsor-investigator's initial receipt of the information about the event.

Other unexpected serious suspected adverse reactions where there is evidence to suggest a causal relationship between the study drug/placebo and the adverse event, will be reported as a serious suspected adverse reaction. This will be reported to the FDA on FDA Form 3500A, no later than 15 calendar days after the sponsor-investigator's initial receipt of the information about the event.

Any clinically important increase in the rate of serious suspected adverse reactions over those listed in the protocol or product insert will be reported as a serious suspected adverse reaction. This will be reported to the FDA on FDA Form 3500A no later than 15 calendar days after the sponsor-investigator's initial receipt of the information about the event.

Findings from other studies in human or animals that suggest a significant risk in humans exposed to the drug will be reported. This will be reported to the FDA on FDA Form 3500A, no later than 15 calendar days after the sponsor-investigators initial receipt of the information about the event.

SAE Reporting to the Sponsor (Eli Lilly and Company)

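### Section 8.3 defines a *reasonable possibility* of relatedness as established causation, so an adverse event rated *possible* in 8.3.1 can be answered *no* in the yes/no field

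*Combined protocol and SAP*

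**What the plan says.** Section 8.3 has the investigator judge, for all AEs, whether there is a *reasonable possibility* of a link to study treatment, device or procedure, weighing the disease and other treatments. It defines that phrase: it "means that there is a cause and effect relationship between the investigational product, study device and/or study procedure and the AE". It then fixes the form of the answer: "The investigator answers yes/no when making this assessment".

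Section 8.3.1, under AE Reporting, lists no/yes items for relationship and also a four-level scale: unrelated, unlikely, possible, probable. The *possible* level reads: "Follows a reasonable temporal sequence from administration but may have been also produced by the patient's clinical state", or by environmental factors or other therapies.

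Other sections set relatedness thresholds of their own. Section 8.2 acts on serious events "considered to be at least possibly related to the study treatment or study participation". Section 8.3.2 sends reports to the FDA "where there is evidence to suggest a causal relationship between the study drug/placebo and the adverse event".

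**The concern.** The definition in 8.3 contains no *may* and no reference to evidence. An investigator who follows it must be able to say that the treatment caused the event. For a *possible* event that cannot be said, because the category itself concedes that something else may be the cause. The literal answer is *no*, while other sections of the same protocol treat the event as related.

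This matters because safety is a stated objective (Study Summary) and the trial has 12 patients and no control arm. There is no comparator rate against which to judge an excess of events, so investigator attribution carries much of the weight in separating drug effects from background. If the yes/no answer is what gets summarised, the error runs in one direction, towards *not related*. Two assessors could also code the same event in opposite ways, each following the text.

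**Working it through.** The plan gives no figure on this point, so the check sets the sections side by side.

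| Section | What it governs | Threshold | Depends on the 8.3 definition? |
|---|---|---|---|
| 8.3 | yes/no relatedness answer for every AE | established causation | yes |
| 8.3.1, AE Reporting | four-level relationship scale | *possible* allows other causes | no |
| 8.1 | related criterion for unanticipated problems | possibly related | no |
| 8.2 | recording of AEs | none: "All adverse events occurring during the study period must be recorded" | no |
| 8.2 | immediate SAE reporting | at least possibly related | no |
| 8.3.1 and 8.5 | SAEs to the company until 30 days after participation ends | none, whatever the cause | no |
| 8.3.1 and 8.5 | SAEs after those 30 days | investigator suspects a causal link | not as written; open to carry-over |
| 8.3.2 | FDA suspected reactions | evidence suggesting a causal link | not as written; open to carry-over |
| 8.4 | stopping rule | possible, probable or definite | no |
| 7.2 | statistical analysis | names no relatedness variable and no table of related AEs | not stated |

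**Tracing one event.** Take an AE with plausible timing and a plausible alternative explanation.

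1. On the 8.3.1 scale it is *possible*.
2. Under 8.1 and 8.4 it counts as related, and under 8.2 too if it is serious.
3. Under the literal wording of 8.3, causation is not established, so the answer can be *no*.
4. No section says which of the four levels correspond to *yes*, so nothing corrects step 3.

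**Size of the effect on a count.** Let N be the number of events that are at least *possible*, and f the share of them rated only *possible*. If those are answered *no* and all the others *yes*, a count from the yes/no field is N × (1 − f). The documents do not give f, so the values below are assumptions:

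- f = 0.25: N × 0.75
- f = 0.50: N × 0.50
- f = 0.75: N × 0.25

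With N = 4, purely as an illustration, the field would show 3, 2 or 1 related events.

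**The case against.** The strongest reply is that little in the plan rests on the faulty sentence. The sentence before it poses a genuine possibility question, and a sensible investigator may answer that one. The four-level rating is collected as well, so a *possible* event stays visible whatever is entered as yes or no. Nearly every reporting trigger states its own, lower threshold. The statistical plan specifies no table built on the yes/no field.

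Most of this stands, and it rules out three stronger readings that a reader might infer.

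- *Possible* events are answered *no*, and related harms therefore go under-reported. The documents state no such mapping. All AEs are recorded, and every SAE within 30 days of the end of participation is reported whatever its cause.
- The early stopping rule loses sensitivity. Section 8.4 expressly counts events attributed as possible, so no loss follows from the rule as written, and any calculation of one would describe a different rule.
- Attribution is the only safety signal. Scheduled laboratory tests and the treatment-interruption guidance in 8.1, which applies whether or not an event is thought related, are further sources.

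The objection does not remove the contradiction. This is a stated rule that gives the wrong answer when followed, not a missing detail. The definition also sits under the heading on SAE reporting, directly after the text on deciding what must be reported. It is therefore foreseeable that staff would apply it when judging whether they suspect causality.

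**Conclusion.** The point holds in a limited form. The definition in 8.3 contradicts the *possible* level in 8.3.1, the possibly-related thresholds in 8.1, 8.2 and 8.4, and the evidence-based wording in 8.3.2. Read literally, it lets an event rated *possible* be answered *no*.

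The consequences reach three places: the yes/no field itself; any summary of related AEs drawn from it; and the two judgement-based triggers, SAEs after 30 days and FDA suspected reactions. The last holds only if staff carry the definition over.

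The proportionate loss in a summary equals the share of related events rated only *possible*. That share is unknown, and the result assumes both that the field is used for counting and that the definition is applied literally. The correction is still worth making, because it removes a one-directional bias from a relatedness answer required for every AE in a single-arm trial with a safety objective.

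**What to change.** In 8.3, replace the definition of *reasonable possibility* with the causality wording already used in 8.3.2 ("where there is evidence to suggest a causal relationship between the study drug/placebo and the adverse event"), leaving out the reference to placebo and keeping the existing mention of device and procedure. Then state the mapping once: possible or probable is *yes*; unlikely or unrelated is *no*. If the label *definite*, which appears in 8.4 but not on the 8.3.1 scale, is kept, it also maps to *yes*. Say that this mapping governs the yes/no field and any summary of related AEs.

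Leave the reporting criteria in 8.3.2 unchanged. The *possible* level needs only a reasonable time sequence and is a lower bar than evidence of a causal link, so mapping it into the FDA criterion would alter that criterion.

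The cost is a short text change and a CRF instruction. The downside is that a few more events will be classed as related.

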8.3.1 Sponsor-Investigator reporting: notifying the Mayo IRB

The sponsor-investigator will report to the Mayo IRB any UPIRTSOs and Non-UPIRTSOs according to the Mayo IRB Policy and Procedures.

Action taken regarding treatment

AE Action:

All adverse events should be treated appropriately. Treatment may include one or more of the following:

- No action taken (i.e. further observation only)
- [study/investigational] treatment dosage adjusted/temporarily interrupted
- [study/investigational] treatment permanently discontinued due to this adverse event
- concomitant medication given
- non-drug therapy given

• patient hospitalized/patient's hospitalization prolonged

AE Outcome:

• All AE outcomes should be recorded (not recovered/not resolved; recovered/resolved; recovering/resolving, recovered/resolved with sequelae; fatal; or unknown)

Serious Adverse Events (SAE)

An SAE is defined as any adverse event (appearance of (or worsening of any pre-existing) undesirable sign(s), symptom(s) or medical conditions(s) which meets any one of the following criteria (Life-threatening in the context of a SAE refers to a reaction in which the patient was at risk of death at the time of the reaction; it does not refer to a reaction that hypothetically might have caused death if more severe.):

- Is fatal or life-threatening
- Results in persistent or significant disability/incapacity
- Constitutes a congenital anomaly/birth defect
- Requires inpatient hospitalization or prolongation of existing hospitalization, unless hospitalization is for:
 - o Routine treatment or monitoring of the studied indication, not associated with any deterioration in condition (specify what this includes)
 - Elective or pre-planned treatment for a pre-existing condition that is unrelated to the indication under study and has not worsened since signing the informed consent
 - Treatment on an emergency outpatient basis for an event not fulfilling any of the definitions of a SAE given above and not resulting in hospital admission
 - O Social reasons and respite care in the absence of any deterioration in the patient's general condition
- Is medically significant, i.e. defined as an event that jeopardizes the patient or may require medical or surgical intervention.

SAE Reporting:

To ensure patient safety, every SAE, regardless of causality, occurring after the patient has provided informed consent and until 30-days after the subject stopped study participation must be reported to Eli Lilly and Company as soon as possible but no later than 5 days from learning of its occurrence according to the Mayo Clinic IRB policy. Any SAEs experienced after the 30-days period should only be reported to Eli Lilly and Company and the Mayo Clinic IRB if the investigator suspects a causal relationship to study treatment. Recurrent episodes, complications, or progression of the initial SAE must be reported as follow-up to the original episode, regardless of when the event occurs. This report must be submitted as soon as possible but no later than 5 days from the investigator receiving the follow-up information. SAE should be followed up until resolution or until it is judged to be permanent. An SAE that is considered completely unrelated to a previously reported one should be reported separately as a new event.

Information collected on the adverse event worksheet (and entered in the research database):

- Subject's name:
- Medical record number:
- Disease/histology (if applicable):
- The date the adverse event occurred:
- Description of the adverse event:
- Relationship of the adverse event to the research (drug, procedure, or intervention*):
- If the adverse event was expected:
- The severity of the adverse event: (use a table to define severity scale 1-5**)
- If any intervention was necessary:
- Resolution: (was the incident resolved spontaneously, or after discontinuing treatment)
- Date of Resolution:

AE Reporting:

Its relationship to the:

- Study treatment (no/yes), or
- Investigational treatment (no/yes), or
- The other study treatment (non-investigational) (no/yes), or
- Both or indistinguishable

The relationship will be categorized as follows:

- Unrelated- Clearly due only to extraneous causes and does not meet criteria listed under possible or probable.
- Unlikely- Does not follow a reasonable temporal sequence from administration. May have been produced by the patient's clinical state or by environmental factors or other therapies administered.
- Possible- Follows a reasonable temporal sequence from administration but may have been also produced by the patient's clinical state, environmental factors or other therapies administered.
- Probable- Clear-cut temporal association with administration with improvement on cessation of investigational medicinal product or reduction in dose. Reappears upon rechallenge. Follows a known pattern of response to the investigational medicinal product.

Its duration (start and end dates) or if the event is ongoing an outcome of not recovered/not resolved should be reported.

Whether it constitutes a serious adverse event (SAE)

Adverse Events (AE):

The severity grade/Common Toxicity Criteria (CTC) AE Version 5.0 grade

- Mild: usually transient in nature and generally not interfering with normal activities
- Moderate: sufficiently discomforting to interfere with normal activities
- Severe: prevents normal activities

If CTCAE grading does not exist for an adverse event, use

1=mild, 2=moderate, 3=severe, 4=life-threatening, CTCAE Grade 5 (death) is not used, but is collected in other CRFs (Study Completion, Death/Survival).

8.3.2 Sponsor-Investigator reporting: Notifying the FDA and Funding Sponsor

The sponsor-investigator will report to the FDA all unexpected, serious suspected adverse reactions according to the required IND Safety Reporting timelines, formats and requirements.

Unexpected fatal or life threatening suspected adverse reactions where there is evidence to suggest a causal relationship between the study drug/placebo and the adverse event, will be reported as a serious suspected adverse reaction. This will be reported to the FDA on FDA Form 3500A, no later than 7 calendar days after the sponsor-investigator's initial receipt of the information about the event.

Other unexpected serious suspected adverse reactions where there is evidence to suggest a causal relationship between the study drug/placebo and the adverse event, will be reported as a serious suspected adverse reaction. This will be reported to the FDA on FDA Form 3500A, no later than 15 calendar days after the sponsor-investigator's initial receipt of the information about the event.

Any clinically important increase in the rate of serious suspected adverse reactions over those listed in the protocol or product insert will be reported as a serious suspected adverse reaction. This will be reported to the FDA on FDA Form 3500A no later than 15 calendar days after the sponsor-investigator's initial receipt of the information about the event.

Findings from other studies in human or animals that suggest a significant risk in humans exposed to the drug will be reported. This will be reported to the FDA on FDA Form 3500A, no later than 15 calendar days after the sponsor-investigators initial receipt of the information about the event.

SAE Reporting to the Sponsor (Eli Lilly and Company)

All Serious Adverse Events ("SAE") required to be reported pursuant to the Protocol shall be provided to Eli Lilly and Company and its representatives by Institution or Principal Investigator within twenty-four (24) hours of learning of the event as well as provide any additional reports agreed upon by the Institution or Principal Investigator and Eli Lilly and Company's contact below. SAE Reports will be sent to the email address provided below. By sending to this e-mail address, the Eli Lilly and Company Pharmacovigilance group and the Eli Lilly and Company clinical operations project manager will receive copies of the reports. This process will be tested and established before the first patient is enrolled in the trial. Notwithstanding anything to the contrary herein, Institution or Principal Investigator will have the primary responsibility of reporting adverse events ("AE") to regulatory authorities.

Copies of IND safety reports submitted to the FDA by the Institution will be shared with the contact below so that these reports can be evaluated and included in investigator brochure or Incyte IND safety submissions as required to ensure safety of other patients who are receiving the product from Eli Lilly and Company for sponsored trials.

Eli Lilly and Company contact for e-mail transmission of individual SAE reports.:

Safety Contacts:

Procedure for Reporting of Pregnancy and Lactation to the Sponsor (Eli Lilly and Company)

Data on fetal outcome are collected for regulatory reporting and drug safety evaluation. Follow-up should be conducted for each pregnancy to determine outcome, including spontaneous or voluntary termination, details of the birth, and the presence or absence of any birth defects, congenital abnormalities, or maternal and/or newborn complications.

8.4 Stopping Rules

The stopping rules specified below are based on the knowledge available at study development. The stopping rule applies to the overall study. We note that the Adverse Event Stopping Rule may be adjusted in the event of either (1) the study re-opening to accrual or (2) at any time during the conduct of the trial and in consideration of newly acquired information regarding the adverse event profile of the treatment(s) under investigation. The study team may choose to suspend accrual because of unexpected adverse event profiles that have not crossed the specified rule below.

Accrual will be temporarily suspended to this study if at any time we observe events considered at least possibly related to study treatment (i.e. an adverse event with attribute specified as "possible", "probable", or "definite") that satisfy the following:

• If 2 or more patients in the first 6 treated patients (or 30% after the first 6 treated patients have been accrued) experience a grade 3 or higher non-hematologic adverse event.

We note that we will review grade 4 and 5 adverse events deemed "unrelated" or "unlikely to be related", to verify their attribution and to monitor the emergence of a previously unrecognized treatment-related adverse event.

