1.5 Dose Rationale

Balancing the safety risks and efficacy data of varying baricitinib doses from prior studies, our study proposes oral Baricitinib (LY3009104) 2 mg QD dosing for 16 weeks (primary endpoint) in LP study subjects. If the patient opts into the extension portion of the study, the dose will escalate to 4 mg.

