3.3 Duration of Participation

The study consists of 3 epochs: screening/washout period (at least 1 week and up to 4 weeks), treatment epoch (16 weeks from screen/washout), and follow up epoch (4 weeks). The screening and washout period will allow for treatment naïve/ new diagnosis LP to undergo evaluation and diagnosis and for treatment refractory to undergo a washout. The total duration of the study will be 21-24 weeks, with the option to enroll in a 3 month extension with a dose escalation to 4 mg for patients who demonstrate response to treatment, but have not yet achieved PGA 0

Tables:

Table-1: Prohibited treatment

Prohibited treatments ^{†,‡}	Washout period (before Randomization Visit)
Any concomitant oral or topical JAK inhibitor	Prohibited
Any biologic drug	Stable dose for 3 months
Immunomodulation treatments for LP§	4 weeks
[e.g., methotrexate, cyclosporine A, corticosteroids (oral, i.v.,	
intramuscular, s.c., intra-articular, transdermal),	
mycophenolate mofetil, azathioprine]	
Topical treatment that is likely to impact signs and symptoms of LP (e.g., pimecrolimus, tacrolimus)	2 weeks
Non-immunosuppressive agents (tetracycline antibiotics & niacinamide)	2 weeks
Prohibited regimen of Topical Corticosteroids (TCS)	
TCS on any location on body (including face, scalp and/or genitoanal area)	2 weeks

[†]If the prohibited treatment is being used during the study for any indication, the subject must discontinue use of the prohibited treatment if he/she wishes to continue in the study.

[‡] In case of undue safety risk for the subject, the subject should discontinue study treatment at the discretion of the investigator/qualified site staff. If the subject received a live virus vaccination during the study, the subject must discontinue study treatment.

§Inhalative CS with only a topical effect (e.g., to treat asthma) are not considered "systemic immunomodulation treatments" and are therefore acceptable as co-medication. Immunosuppressive medication for conditions other than LP will be allowed.

Table 2: Washout Periods for Monoclonal Antibodies (Biologic Drugs)

Brand	Generic Name	Recommended Minimum
Name		Washout (approximately 5 half-lives)
ACTEMRA	Tocilizumab	8 weeks
CIMZIA	Certolizumab pegol	10 weeks
COSENTYX	Secukinumab	16 weeks
DUPIXENT	Dupilumab	12 weeks
ENBREL	Etanercept	4 weeks
HUMIRA	Adalimumab	8 weeks
KEVZARA	Sarilumab	7 weeks
ORENCIA	Abatacept	8 weeks
REMICADE	Infliximab	6 weeks
RITUXIN	Rituximab	6 months
SIMPONI	Golumimab	10 weeks

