5.7.3 Dispensing of Study Drug

Regular study drug reconciliation will be performed to document drug assigned, drug dispensed, drug returns, and drug remaining. This reconciliation will be logged on the drug reconciliation form and signed and dated by the study team. A three month extension and dose excalation to 4mg will be available to all patients who demonstrate response to treatment, but have not yet achieved PGA 0

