8.5 Medical Monitoring

It is the responsibility of the Principal Investigator to oversee the safety of the study at his/her site. This safety monitoring will include careful assessment and appropriate reporting of adverse events as noted above, as well as the construction and implementation of a site data and safety-monitoring plan (see section 10 "Study Monitoring, Auditing, and Inspecting"). Medical monitoring will include a regular assessment of the number and type of serious adverse events.

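### As written, the Section 8.4 stopping rule counts 4 mg extension events but can only suspend accrual, so crossing it neither pauses escalation to 4 mg nor triggers review of patients on 4 mg

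*Combined protocol and SAP*

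**What the plan says.** **The rule (Section 8.4).** Its scope is stated directly: "The stopping rule applies to the overall study". The trigger is "If 2 or more patients in the first 6 treated patients (or 30% after the first 6 treated patients have been accrued") with a grade 3 or higher non-hematologic event. The action is "Accrual will be temporarily suspended to this study if at any time we observe events considered at least possibly related to study treatment" and the trigger is met. The section also lets the team suspend accrual before the rule is crossed, allows the rule to be adjusted at any time as adverse event information accumulates, and provides for checking the attribution of grade 4 and 5 events called unrelated or unlikely.

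**The dose step.** Section 5.2 gives 2 mg daily from Day 0 to Week 16. Section 1.5 adds: "If the patient opts into the extension portion of the study, the dose will escalate to 4 mg". Section 3.3 describes the study "with the option to enroll in a 3 month extension with a dose escalation to 4 mg", and Section 5.7.3 says that the extension "will be available to all patients who demonstrate response to treatment, but have not yet achieved PGA 0". None of these sections refers to 8.4 or sets a safety condition for escalating.

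**Enrolment.** Section 3.2 fixes 12 subjects, and Section 4.4.1 says that withdrawn subjects are not replaced.

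**Other safety provisions.** Section 8.1 has laboratory-based interruption and discontinuation criteria for individual patients. Section 8.3.1 lists dose adjustment, interruption and discontinuation among the responses to an adverse event. Section 8.5 calls for a site safety-monitoring plan and says "Medical monitoring will include a regular assessment of the number and type of serious adverse events". Section 8.3.2 requires a report to the FDA of "Any clinically important increase in the rate of serious suspected adverse reactions".

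**The concern.** The extension doubles the dose, and the events that it may produce already count towards the one numeric study-level rule. The action attached to that rule, however, bears on a different group. If 4 mg events cross it, new patients are kept off 2 mg while patients reaching Week 16 can still move up to 4 mg and those already on 4 mg carry on. Because 4 mg cannot start before Week 16, its exposure comes late, and much or all of it may come when there is no accrual left to suspend. What is at stake is whether a study-level safety signal leads to any required action on the higher dose.

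**Working it through.** The protocol gives no operating characteristics for the rule, so there is no stated figure to reproduce. The check is a comparison of texts, a timing calculation and a short look at pooling.

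**1. Texts side by side**

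| Question | Section 8.4 | Sections 1.5, 3.3, 5.7.3 |
|---|---|---|
| Are 4 mg events counted? | Yes: overall study, any time, no split by dose | – |
| Mandatory action | Suspend accrual | – |
| Discretionary action | Suspend accrual | – |
| Condition for 4 mg | None stated | Response, not yet PGA 0, patient opts in |
| Review of patients on 4 mg after a crossing | None stated | None stated |

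**2. When the action runs out**

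Inputs from the protocol: 12 patients, no replacement, escalation at Week 16, a 3-month extension. I take the extension as 12 weeks, which fits the schedule in Table-3 (drug at Weeks 16, 20 and 24, none at Week 28). Accrual time A is not stated, so I assume 16, 26 and 52 weeks with even spacing. I also assume that extension uptake is unrelated to enrolment order.

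- Enrolment times: t_i = A × i/11, for i = 0 to 11.
- 4 mg runs from t_i + 16 to t_i + 28.
- The escalation point falls at or after the last enrolment if t_i ≥ A − 16.
- Weeks of 4 mg after the last enrolment: min(12, max(0, t_i + 28 − A)), out of 12 × 12 = 144.

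Results:

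- A = 16: the condition is t_i ≥ 0, so 12 of 12 escalation points. Exposure is 144/144 = 100%.
- A = 26 (spacing 2.364): t_i ≥ 10 holds for i = 5 to 11, so 7 of 12. Weeks are 2.00 + 4.36 + 6.73 + 9.09 + 11.45 + 7 × 12 = 117.64 (terms unrounded), and 117.64/144 = 82%.
- A = 52 (spacing 4.727): t_i ≥ 36 holds for i = 8 to 11, so 4 of 12. Weeks are 4.36 + 9.09 + 4 × 12 = 61.45, and 61.45/144 = 43%.

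Treating enrolment as continuous gives nearly the same. The share of 4 mg exposure while accrual is open is 0% at 16 weeks, (10²/2)/(12 × 26) = 16% at 26 weeks and (24 + 6)/52 = 58% at 52 weeks, which leaves 100%, 84% and 42% afterwards. None of this depends on an event rate.

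**3. Pooling**

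The 30% clause needs the smallest whole number at or above 0.30 × n: 3 patients at n = 7 to 10 and 4 at n = 11 or 12. If 3 of 6 patients on 4 mg have a qualifying event and nobody on 2 mg does, the 4 mg rate is 3/6 = 50% but the overall rate is 3/12 = 25%, which does not meet the 30% clause. It would still meet the first-6 clause if two of the three were among the first six treated and that clause remains live. The text does not say whether it does.

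The size of the dilution varies widely. For illustration, assume 12 treated, 6 entering the extension, a 4 mg event rate of 1/3 and no 2 mg events. The probability of crossing is then:

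- 30% clause only: P(Bin(6, 1/3) ≥ 4) = 73/729 = 10%.
- Both clauses live, entrants split three and three: P(first-six count ≥ 2, or total ≥ 4) = 7/27 + (12/27)(1/27) = 28%.
- Both clauses live, all entrants among the first six: P(Bin(6, 1/3) ≥ 2) = 473/729 = 65%.

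A 2-of-6 limit counted on 4 mg patients alone also gives 65%. The loss from pooling therefore runs from about 55 percentage points to none, depending on facts that the documents do not give.

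**The case against.** **The rule can be adjusted at any time in light of new adverse event information.** This is true, and the power does not lapse at the twelfth enrolment. It is permission to change the rule, though, and does not prescribe an action on 4 mg. It does mean that only the mandatory action loses its object.

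**Suspending accrual might cover enrolment into the extension, which Section 3.3 frames as an option to enrol.** That reading is strained, since 8.4 uses the word for patients entering the study. Even if accepted, it would not reach patients already on 4 mg.

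**The patients are not unprotected.** A reader might infer that nobody watches patients on 4 mg. The documents do not support that. Adverse events and laboratory values are checked at Weeks 20, 24, 28 and 32, individual interruption and discontinuation provisions apply, serious events are assessed regularly, and a site safety plan is required. Entrants have also had 16 weeks on 2 mg. This stands and limits the severity.

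**4 mg has not been shown to be more harmful.** A reader might infer otherwise from the lupus study, where interruptions for adverse events were 6.7% at 2 mg and 20.2% at 4 mg (placebo 10.5%), or from phase 2 atopic dermatitis, where discontinuations for adverse events were 8% and 16% (placebo 10%). Section 1.4 also reports lupus serious adverse events of 10.5% at 2 mg and 9.6% at 4 mg (with serious infections 1.9% and 5.8%), no difference between doses in rheumatoid arthritis through 16 weeks, and 1% at both doses in phase 3 atopic dermatitis. The evidence is mixed, and none of it is a related grade 3 or higher rate in lichen planus.

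**A separate 4 mg threshold is a design preference in a 12-patient estimation study.** A reader might infer from the pooling figures that such a threshold is required. The figures rest on assumed uptake, entry order and high event rates, and the gap vanishes in one scenario. This objection stands.

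**Conclusion.** The gap holds as a mismatch between what the rule counts and what it does. It follows from the text of 8.4, 1.5, 3.3 and 5.7.3 and needs no assumption about event rates. Its reach in time depends on an unstated accrual period: with even accrual over 16 to 52 weeks and 12 weeks on 4 mg, between 100% and 43% of 4 mg exposure comes after the mandatory action has nothing left to act on. Dilution by pooling is possible but cannot be sized from the documents. Severity is low to moderate, because patient-level safeguards and the freedom to adjust the rule remain.

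**What to change.** In Section 8.4, add that crossing the rule at any time, including after accrual closes, also suspends further escalation to 4 mg and triggers a review of every patient on 4 mg, with a decision to continue, return to 2 mg or stop. State as well that the first-6 clause stays in force after patient 7.

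The cost is a short addition to one section, with no new visits, tests or data. The downside is that a crossing caused by 2 mg events would also pause an optional escalation.

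A separate 4 mg threshold, such as 2 of the first 6 patients starting 4 mg, is optional. With 6 entering, it would pause escalation with probability P(Bin(6, 0.05) ≥ 2) = 3% if the true 4 mg rate is 5%, and P(Bin(6, 0.10) ≥ 2) = 11% if it is 10%. Whether that price is worth paying is for the study team to judge.
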